7.3.2 Demographics and Baseline Characteristics

The following demographic and baseline characteristics will be summarized by treatment group. All baseline presentations will identify subjects with missing measurements. Listings will also be provided.

- Age (descriptive statistics)
- Age category I (< 65, ≥ 65)
- Age category II (< 65, ≥ 65 - < 75, ≥ 75)
- Sex (Male vs. Female)
- Race (White, Black, Asian, American Indian or Alaska Native, Native Hawaiian or other Pacific Islander, Other)
- Region (US/Canada, Europe, Rest of the World)
- Disease diagnosis (Glioblastoma, Gliosarcoma)

- RPA Class (III, IV, V, Other)
- Type of Surgery (Complete Resection, Partial Resection, Other)
- Baseline Karnofsky performance status (100%, 95%, 90%, 80%, ...)
- Weight, BSA (descriptive statistics)
- Gene Promoter Methylation (Methylated, Unmethylated, Indeterminate, Not reported)
- Smoking Status (Current/Former, Never, Unknown, Not Reported)
- Baseline Corticosteroid Use (Based on average corticosteroid use 5 days prior to start of dosing (randomization date for subjects not treated))
- Time from Initial Disease Diagnosis to Randomization (in weeks) (Median, Range)
- All lesions (Investigator Tumor Assessments at Baseline): sites of disease, number of disease sites per subject.
- Measurable lesions (Investigator Tumor Assessments at Baseline): Presence of measurable lesions, site of measurable lesion, sum of products of perpendicular diameters of measurable lesions.
- Pre-treatment events: summarized by worst CTC grade presented by SOC/PT

Summary table (cross-tabulation) by treatment group for stratification factor (extent of tumor resection: complete vs partial) will be provided to show any discrepancies between what was reported through IVRS vs. CRF at baseline. This summary will be performed based on all randomized subjects.

A listing of randomization scheme presenting randomized treatment group and as treated treatment group will be provided for all randomized subjects.

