3.1.2 Treatment Phase

3.1.2.1 Randomization and Initiation of Treatment

After eligibility has been confirmed, subjects who are clinically ready to begin study treatment (ie, recovered from surgery) will proceed to the treatment phase of the study via a second call into the IVRS system. At this call, subjects will be randomized 1:1 to receive radiotherapy plus nivolumab (RT + nivolumab) or radiotherapy plus temozolomide (RT + TMZ).

Randomization will be prospectively balanced (ie, stratified) according to post-operative MRI finding of “complete” versus “partial” resection. For the purposes of this study, a complete resection will be defined as ≤ 5 mm of contrast enhancement on T1 images of the post tumor surgical region following surgical resection. A partial resection is defined as ≥ 10 mm of residual contrast-enhancing tumor tissue on T1 images following surgical resection. Resections with a residual of between > 5 and < 10 mm of enhancement will be defined as partial or complete by the investigator’s best clinical judgment.

The total time elapsed from diagnostic surgery to initiation of RT should not exceed 42 days, including a maximum of 7 days from randomization to initiation of RT; however, treatment may be delayed if clinically required. Subjects in the RT + nivolumab arm should begin nivolumab within 7 days after randomization, and may be given at any time prior to RT start, as clinically appropriate. Subjects randomized to the RT + TMZ arm will begin combination chemoradiotherapy on the same day, within 7 days after randomization, as clinically appropriate.

See [sections 4.5.1](#) and [4.5.2](#) for details of dosing for nivolumab and temozolomide; for an overview of the treatment phase, see [Section 3.1.2](#).

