2.3 Blinding and Unblinding

Not applicable. This is an open-label study.

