4 ENDPOINTS

4.1 Primary

The primary endpoint is OS. OS is defined as the time between the date of randomization and the date of death due to any cause. A subject who has not died will be censored at the last known alive date.

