6 STUDY PERIODS, TREATMENT REGIMENS AND POPULATIONS FOR ANALYSES

6.1 Study Periods

- Baseline period:
 - Baseline evaluations or events will be defined as evaluations or events that occur before the date and time of the first dose of study treatment. Evaluations (laboratory tests, pulse oximetry and vital signs) on the same date and time of the first dose of study treatment will be considered as baseline evaluations.
 - In cases where the time (onset time of event or evaluation time and dosing time) is missing or not collected, the following definitions will apply:
 - ◆ Pre-treatment AEs will be defined as AEs with an onset date prior to but not including the day of the first dose of study treatment
 - ◆ Baseline evaluations (laboratory tests, pulse oximetry and vital signs) will be defined as evaluations with a date on or prior to the day of first dose of study treatment
 - If there are multiple valid assessments on or prior to the first dose of study treatment:
 - ◆ For laboratory tests, the latest non missing labs value on or before first dose date (and time if collected) will be used as the baseline in the analyses. For 'LIPASE' and 'GLUCOSE', for treated subjects only, the last predose assessment with non-missing toxicity grade will be considered as baseline. If multiple assessments exist with the same collection date (and time if collected) and entry date and time, then the first observation is used as baseline.

- 
- 
- 
- Post baseline period:
 - On-treatment AEs will be defined as AEs with an onset date and time on or after the date and time of the first dose of study treatment (or with an onset date on or after the day of first dose of study treatment if time is not collected or is missing). For subjects who are off study treatment, AEs will be included if event occurred within a safety window of 30 days (or 100 days depending on the analysis) after the last dose of study treatment. No “subtracting rule” will be applied when an AE occurs both pre-treatment and post-treatment with the same preferred term and grade.
 - On-treatment evaluations (laboratory tests, pulse oximetry and vital signs) will be defined as evaluations taken after the day (and time, if collected and not missing) of first dose of study treatment. For subjects who are off study treatment, evaluations should be within a safety window of 30 days (or 100 days depending on the analysis) after the last dose of study treatment.

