7.5.1.2 OS sensitivity Analyses

The following OS sensitivity analyses will be performed:

- 1) OS will be compared between treatment groups using a two-sided unstratified log-rank test.
- 2) OS will be compared between the treatment groups using the strata as determined at baseline (CRF source). This analysis will be performed only if stratification variable at IVRS and at baseline disagree for at least 10% of the randomized subjects.
- 3) OS will be compared between the treatment groups using a two-sided stratified log-rank test in All treated subject population, using arm, as randomized. This analysis will be performed only if the proportion of randomized but never treated subjects exceeds 5%.
- 4) A multivariate Cox regression model will be used to estimate the treatment effect after including the following covariates measured at baseline: Backward selection method will be used to eliminate non-significant covariates at level 0.15.
 - a) Age (continuous covariate)
 - b) Steroid Use (Yes, No)
 - c) Performance Status (Karnofsky scale) (≤ 80 , > 80)

The level of the covariate normally associated with the worst prognosis will be coded as the reference level. The hazard ratio associated with treatment and with each of the baseline covariates will be presented along with associated 95% CIs.

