7.5.1.3 Consistency of Treatment Effect on OS in Subsets

To assess consistency of treatment effects in different subsets, a “forest” plot of the OS hazard ratio (and 95% CI) will be produced for the following variables, but not limited to:

- Baseline measurable lesion (yes vs. no) (source: CRF)
- Region (US/Canada vs. Europe vs. Rest of World)
- Age categorization (< 65 , $\geq 65 - < 75$, ≥ 75 , ≥ 65)
- Age categorization (< 50 , $\geq 50 - < 65$)
- Gender (Male vs. Female)
- Race (White, African American, Asian, Other)
- RPA class (III, IV, V, other)
- Smoking status (yes vs. no, unknown)
- Baseline Performance Status (Karnofsky scale) (≤ 80 , > 80)
- Baseline Pathology (Glioblastoma vs. Gliosarcoma)
- Baseline Corticosteroid use (No, Yes)

If a subgroup category has less than 10 subjects in a treatment group, then HR will not be reported for that subgroup.

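### Baseline steroid use is measured from first dose, so it can fall after open-label randomization, and no other definition is visible for the steroid covariate and subgroup in the OS analyses (minor)

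*SAP*

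**What the plan says.** - **Steroid window.** The baseline list in SAP 7.3.2 has "Baseline Corticosteroid Use (Based on average corticosteroid use 5 days prior to start of dosing (randomization date for subjects not treated". Treated subjects are anchored at first dose and untreated subjects at randomization.
- **General baseline rule.** SAP 6.1 uses the same anchor: baseline evaluations are "defined as evaluations or events that occur before the date and time of the first dose of study treatment".
- **Time origin of the endpoint.** SAP 4.1: "OS is defined as the time between the date of randomization and the date of death due to any cause".
- **Blinding.** SAP 2.3: "This is an open-label study".
- **Gap between the two anchors.** Protocol 3.1.2.1 limits the time from surgery to RT, "including a maximum of 7 days from randomization to initiation of RT; however, treatment may be delayed if clinically required". Nivolumab is to start within 7 days of randomization and may precede RT. Temozolomide starts on the same day as RT, also within 7 days.
- **Use in OS analyses.** SAP 7.5.1.2, item 4, fits a Cox model to "estimate the treatment effect after including the following covariates measured at baseline", one of which is "Steroid Use (Yes, No", with backward elimination at the 0.15 level. The forest plot in SAP 7.5.1.3 has a row "Baseline Corticosteroid use (No, Yes". Neither section gives a window, a rule for Yes versus No, or a reference to 7.3.2.

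**The concern.** A covariate or subgroup variable in an as-randomized survival comparison should be fixed before allocation, because only then does randomization balance it. Here the only visible steroid definition, and the general baseline rule behind it, permit a value recorded after both investigator and patient know the arm. It also gives one variable two time origins, depending on whether the subject was treated.

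If recorded steroid use shifts differently by arm between randomization and first dose, subjects with the same prognosis are classified differently in the two arms. The covariate-adjusted OS HR and the HRs within steroid subgroups are then biased, in a direction that cannot be known in advance. Two routes are possible. One is prescribing that responds to the known assignment; Protocol 3.4.3 permits steroids for GBM symptoms. The other is timing: the start rules differ by arm, so the windows could sit at different distances from randomization. If tapers were still running, recorded use would then differ without any arm-driven prescribing.

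At stake are one of four OS sensitivity analyses and one forest-plot row, whose purpose is to test how robust the primary result is.

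**Working it through.** **1. The plan's own figure.** With HR 0.72, two-sided alpha 0.05, 90% power and 1:1 allocation (SAP 5):

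events = 4(1.960 + 1.282)² / (ln 0.72)² = 42.0 / 0.1079 ≈ 390.

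The critical HR is exp(−1.960 × 2/√390) = 0.82. Both match the SAP. The primary test stratifies only by extent of resection, so nothing below alters them. The SE of the log HR at 390 deaths is 2/√390 = 0.101.

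**2. Window days after randomization.** Let randomization be day 0 and first dose day g. The window is days g−5 to g−1, so the number of window days after day 0 is min(5, max(0, g−1)).

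| First dose (days after randomization) | 0–1 | 2 | 3 | 4 | 5 | 6 or more |
|---|---|---|---|---|---|---|
| Post-randomization days of 5 | 0 | 1 | 2 | 3 | 4 | 5 |

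A start on day 6 or 7, inside the permitted interval, makes the whole window post-allocation. Anchoring at randomization gives 0 for every g.

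**3. Effect on the HRs (illustration).** These assumptions are not in the documents: true treatment HR 1.00, 40% steroid users, steroid HR for death 1.5 to 2.0, Yes meaning any use, and misrecording in one arm only. From SAP 5: exponential survival with median 13.0 months (applied here overall), uniform accrual over 10 months, analysis at 33 months.

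Groups are formed by arm, prognosis and recorded steroid use. The large-sample Cox estimate is the pair (β for treatment, γ for recorded use) that sets the expected score to zero: the sum over time of expected deaths × (covariate − risk-set mean) = 0, with risk-set means weighted by exp(β·arm + γ·recorded use). Subgroup HRs solve the same equation for β alone within recorded users or non-users. Age, Karnofsky status and the resection stratum are left out.

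Three kinds of change are considered:
- **A:** users recorded as non-users.
- **B1:** non-users recorded as users, prognosis unchanged.
- **B2:** as B1, but the subjects concerned have users' prognosis. The same share has that prognosis in the other arm, where it goes unrecorded.

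| Case | Share changed | Adjusted HR, change in nivolumab arm | Adjusted HR, change in TMZ arm | Affected subgroup HR (nivolumab / TMZ arm) |
|---|---|---|---|---|
| A | 2% of users | 1.0029–1.0047 | 0.9953–0.9971 | non-users 1.0052–1.0088 / 0.9913–0.9948 |
| A | 5% of users | 1.0073–1.0117 | 0.9885–0.9928 | non-users 1.0128–1.0216 / 0.9788–0.9873 |
| B1 | 2% of non-users | 0.9897–0.9945 | 1.0055–1.0104 | users 0.9784–0.9878 / 1.0123–1.0220 |
| B1 | 5% of non-users | 0.9752–0.9867 | 1.0134–1.0254 | users 0.9495–0.9711 / 1.0297–1.0532 |
| B2 | 2% of non-users | 0.993–0.996 | 1.004–1.007 | non-users 0.987–0.992 / 1.008–1.013 |
| B2 | 5% of non-users | 0.983–0.989 | 1.011–1.017 | non-users 0.967–0.980 / 1.020–1.034 |

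The unadjusted HR is 1.000 throughout. In SE units the largest adjusted shifts are |ln 0.9897|/0.101 = 0.10 at 2% and |ln 0.9752|/0.101 = 0.25 at 5%. Varying users from 20% to 60% raises these to 0.14 (HR 0.9858 or 1.0144) and 0.32 (HR 0.9677 or 1.0334). Three simulations of 200,000 subjects for B1 at 5%, steroid HR 2.0, change in the nivolumab arm, gave adjusted HRs of 0.973 to 0.976 against 0.975 computed.

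**4. What those shares require.** Case A needs the last steroid by day 0 for a day-6 start, or by day 1 for a day-7 start. Cases B1 and B2 need one new start on a post-randomization window day. If first-dose days were uniform over 0 to 7 (assumption), 2/8 = 25% of subjects start on day 6 or 7, and 6/8 = 75% on day 2 or later. In the affected arm, case A at 2% or 5% then needs 0.02/0.25 = 8% or 0.05/0.25 = 20% of the day 6–7 users. The new-start cases need 0.02/0.75 = 2.7% or 0.05/0.75 = 6.7% of non-users starting on day 2 or later.

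**The case against.** The strongest reply is that the link from the baseline table to the OS analyses is inferred. Parts of SAP 6.1 and of the concomitant-medication section are redacted, and the Conventions section is not in the public text; any of these could define steroid use for modelling. The Cox covariate carries a different name from the table entry, and the table describes an average, not a Yes/No variable. This stands as a limit: only the absence of another definition from the visible text can be claimed. It does not remove the point, because the one visible definition and the general baseline rule share the first-dose anchor.

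Second, no between-arm mechanism is shown. The window closes before dosing, so study drug cannot act on it. Protocol 3.1.1 and 3.4 place the taper before randomization, and no arm-specific steroid rule appears. This also stands, and it is why the effect is probably small. Differing start rules by arm do leave a route through timing alone.

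Third, the larger illustrated shifts are generous. B1 assumes that new starters keep non-user prognosis, which fits poorly with starting steroids for tumor symptoms; under B2 the largest shift is about 0.17 SE at 5% and 0.07 SE at 2%. Case A at 5% needs an implausible cluster of stops around day 0. Backward elimination may also drop the covariate. All of this is fair, and it bears on size, not on whether the definition is sound.

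Finally, the gap categories above 7 days in SAP 7.4.1 are reporting bins and do not show that long delays are common.

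**Conclusion.** The point holds and is minor. For treated subjects the visible definition allows some or all of the baseline steroid window to fall after open-label randomization, within the permitted start interval. By inference this reaches OS sensitivity analysis 4 and the steroid row of the OS forest plot.

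Any bias is likely small and of unknown direction. At 40% users with 2% to 5% misrecorded in one arm, the adjusted HR shifts by at most 0.10 to 0.25 SE. With no between-arm difference in recorded use, there is no such bias. These sizes rest on assumed steroid prevalence, prognostic strength, Yes/No cut and misrecording; the documents give none of these, nor the distribution of the gap to first dose. The primary stratified log-rank test, its HR, the power and the gate to PFS testing do not use steroid status and are unaffected.

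**What to change.** In SAP 7.5.1.2(4) and 7.5.1.3, define steroid use for all randomized subjects from the five days up to the randomization date, the anchor that 7.3.2 already applies to untreated subjects. The same sentence should say how the five-day value becomes Yes or No. If a definition elsewhere in the SAP already does this, cite it in both places. The pre-dose average can stay in 7.3.2 as a descriptive summary, labelled so that its counts are not expected to match the forest plot.

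The cost is one sentence in two sections. No new data are needed: screening records steroid dose within 14 days before randomization (Protocol Table 5.1-1), dose at randomization is checked for eligibility (Protocol 3.3.1), and steroid doses with start and stop dates are collected before and during the study (Protocol 3.4.3).

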7.3.3 Medical History

General medical history will be listed by subject.

7.3.4 Prior Therapy

The following will be summarized by treatment group.

- Prior systemic cancer therapy (yes/no)
- Prior agent received (generic name)
- Prior surgery related to cancer (yes/no)
- Prior radiotherapy (yes/no)

Prior systemic cancer therapy agents and medication will be reported using the generic name. A summary table by ATC class and generic name and a listing by subject will also be provided including prior/current non study medication.

7.3.5 Baseline Examinations

Subjects with abnormal baseline physical examination will be listed by subject and will be tabulated by examination criteria (e.g. neck, cardiovascular, lungs, etc.), by treatment group.

7.4 Extent of Exposure

Listings will include all available exposure data. Analyses will be performed by treatment group “as treated” in all treated subjects, unless otherwise specified.

7.4.1 Administration of Study Therapy

The following parameters will be summarized (descriptive statistics) by treatment group:

- Time from randomization and to first dose of study therapy (0 to 3 days, > 3 to 7, > 7 to 14, > 14 to 21, > 21 to 28, > 28)

Nivolumab

Dose (mg) is defined as total Dose administered (mg) and is collected on the CRF.

Cumulative Dose (mg) is sum of all the doses (mg) administered to a subject.

Duration of Treatment (in months): (Last dose date - Start dose date + 1) / 30.4375

Relative dose intensity (%): Sum of all relative dose intensity for all cycles/N where N is the number of cycles of nivolumab administered.

For each cycle i:

Cycle duration (i)(wk) = (dose date(i+1)-dose date (i))/7, when ith cycle is not the last.

Cycle duration (i)(wk) = 2, for the last cycle if ≤ 8 doses are taken.

Cycle duration (i)(wk) = 4, for the last cycle if > 8 doses are taken

Dose Intensity for cycle i (mg/wk) = Dose (i) / Cycle duration (i)

Relative Dose intensity for cycle i (%) = (Dose Intensity for cycle i (mg/wk) / 120(mg/wk))*100

The following parameters will be summarized (descriptive statistics) for subjects treated with nivolumab:

- Number of doses received
- Cumulative dose
- Relative dose intensity (%) using the following categories:

< 50%; 50 - < 70%; 70 - < 90%; 90 - < 110%; ≥ 110%.

Duration of treatment will be presented by treatment group using a Kaplan-Meier curve. The last dose date will be the event date for those subjects who are off study therapy. Median duration of treatment and associated 95% CI will be provided. Subjects who are still on study therapy will be censored on their last dose date.

Temozolomide

Duration of Treatment (in weeks): (Dose end date - Dose start date + 1) / 7

Dose (mg/m²): total dose administered (in mg)/BSA at baseline (m²). Dose administered in mg at each dosing date is collected on the CRF

Cumulative dose (in mg/m²): sum of all the doses (mg/m²) administered to a subject

The following parameters will be summarized (descriptive statistics) by phase (induction and maintenance) for subjects treated with temozolomide:

- Duration of Treatment (in weeks)
- Cumulative dose (in mg/m²)
- Number of subjects that received less than 90% of planned dose

For maintenance phase only

- Number of subjects with dose escalation to 200mg/m²

For nivolumab and temozolomide: a by-subject listing of dosing of study medication (record of study medication, infusion details, and dose changes) and a listing of batch numbers will be also provided.

Radiotherapy

Duration of radiotherapy (in weeks): (Dose end date - Dose start date + 1) / 7

Cumulative dose (in Gy): sum of all the doses (Gy) administered to a subject as per CRF.

The following parameters will be summarized:

- Duration of radiotherapy (in weeks)
- Cumulative dose (in Gy)
- Number of subject that received less than 90% of planned dose

7.4.2 Modifications of Study Therapy

7.4.2.1 Nivolumab Dose delays

Each nivolumab infusion may be delayed. A dose will be considered as actually delayed if the delay is exceeding 3 days (i.e. greater than or equal to 4 days from scheduled dosing date) for nivolumab. Reason for dose delay will be retrieved from CRF dosing pages.

The following parameters will be summarized:

- Number of subjects with at least one dose delayed, number of dose delayed per subject, Length of Delay and Reason for Dose Delay

7.4.2.2 Nivolumab Infusion Interruptions and Rate Changes

Each nivolumab infusion can be interrupted and/or the IV infusion rate can be reduced. This information will be retrieved from CRF dosing pages

The following parameters will be summarized for subjects treated with nivolumab:

- Number of subjects with at least one dose infusion interruption, number of infusion interruptions per subject and the reason for interruption.
- Number of subjects with at least one IV infusion rate reduction, number of IV infusion rate reduction per subject and the reason for reduction

7.4.2.3 Temozolomide Dose Modifications

The following parameters will be summarized by phase (induction and maintenance) for subjects treated with temozolomide:

- Number of subjects with at least one dose modification and reasons for dose modification.

7.4.2.4 Missing Radiotherapy

The number of subjects with at least one dose of radiotherapy missed and the reasons for missing dose will be tabulated for subjects treated with radiotherapy.

